## 5 Investigational Plan

### 5.1 Overall Trial Design and Plan

This is a multicenter, open-label, international, Phase I/II study to evaluate the dose, safety and tolerability, antitumor activity, PK, and pharmacodynamics of avelumab in pediatric subjects 0 to < 18 years of age with refractory or relapsed malignant solid tumors (including central nervous system tumors) and lymphoma for which no standard therapy is available or for which the subject is not eligible for the existing therapy.

The study will consist of 2 parts: the dose-finding part (Phase I) and the tumor-specified expansion part (Phase II). During Phase I, the RP2D of avelumab in children will be determined. During Phase II, 2 expansion cohorts will be enrolled, with specific tumors chosen based on available data from the Phase I part of the study, ongoing studies with avelumab and other ICIs, clinical and nonclinical chemotherapy combination data, and any published literature.

[figure not shown]

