**Table 5 Management of Immune-related Adverse Events**

Gastrointestinal irAEs		
Severity of Diarrhea/Colitis (NCI-CTCAE v4.03)	Management	Follow-up
Grade 1 Diarrhea: < 4 stools/day over Baseline Colitis: asymptomatic	Continue avelumab therapy Symptomatic treatment, eg, loperamide)	Close monitoring for worsening symptoms Educate subject to report worsening immediately If worsens: Treat as Grade 2, 3, or 4
Grade 2 Diarrhea: 4 to 6 stools per day over Baseline; iv fluids indicated < 24 hours; not interfering with ADL Colitis: abdominal pain; blood in stool	Delay avelumab therapy Symptomatic treatment	If improves to Grade 1: Resume avelumab therapy  If persists > 5 to 7 days or recurs: Treat as Grade 3 to 4
Grade 3 to 4 Diarrhea (Grade 3): ≥ 7 stools per day over Baseline; incontinence; iv fluids ≥ 24 hours; interfering with ADL Colitis (Grade 3): severe abdominal pain, medical intervention indicated, peritoneal signs Grade 4: life-threatening, perforation	Withhold avelumab for Grade 3 Permanently discontinue avelumab for Grade 4 or recurrent Grade 3. 1.0 to 2.0 mg/kg/day prednisone or equivalent Add prophylactic antibiotics for opportunistic infections Consider lower endoscopy	If improves: Continue steroids until Grade 1, then taper over at least 1 month, resume avelumab therapy following steroids taper (for initial Grade 3).  If worsens, persists > 3 to 5 days, or recurs after improvement: Add infliximab 5 mg/kg (if no contraindication), Note: Infliximab should not be used in cases of perforation or sepsis
Dermatological irAEs		
Grade of Rash (NCI-CTCAE v4.03)	Management	Follow-up
Grade 1 to 2 Covering ≤ 30% body surface area	Continue avelumab therapy Symptomatic therapy (eg, antihistamines, topical steroids)	If persists > 1 to 2 weeks or recurs: Withhold avelumab therapy Consider skin biopsy Delay avelumab therapy Consider 0.5 to 1.0 mg/kg/day prednisone or equivalent. Once improving, taper steroids over at least 1 month, consider prophylactic antibiotics for opportunistic infections, and resume avelumab therapy following steroids taper If worsens: Treat as Grade 3 to 4

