Grade 2 AST or ALT > 3.0 to ≤ 5 x ULN and/or total bilirubin > 1.5 to ≤ 3 x ULN	Withhold avelumab therapy Increase frequency of monitoring to every 1 to 2 days	If returns to Baseline: Taper steroids over at least 1 month, consider prophylactic antibiotics for opportunistic infections, and resume avelumab therapy following steroids taper.

	
1.0 to 2.0 mg/kg/day prednisone or equivalent. Add prophylactic antibiotics for opportunistic infections Consult gastroenterologist/hepatologist Consider obtaining MRI/CT scan of liver and liver biopsy if clinically warranted
	If worsens: Treat as Grade 3-4.

Grade 3 to 4 AST or ALT > 5 x ULN and/or total bilirubin > 3 x ULN
	
Discontinue avelumab therapy Increase frequency of monitoring to every 1 to 2 days 1.0 to 2.0 mg/kg/day methylprednisolone iv or iv equivalent Add prophylactic antibiotics for opportunistic infections Consult gastroenterologist Consider obtaining MRI/CT scan of liver and liver biopsy if clinically warranted (for trial sites in Germany, only MRI is to be used)
	
If returns to Grade 2: Taper steroids over at least 1 month If does not improve in > 3 to 5 days, worsens or rebounds: Add mycophenolate mofetil 600 mg/m^2 (for subjects 2 to 18 years of age) twice daily If no response within an additional 3 to 5 days, consider other immunosuppressants per local guidelines

Renal irAEs		
Grade of Creatinine Increased (NCI-CTCAE v4.03)	Initial Management	Follow-up Management

Grade 1 Creatinine increased > ULN – 1.5 x ULN
	Continue avelumab therapy	Continue renal function monitoring If worsens: Treat as Grade 2 to 3 or 4

Grade 2 to 3 Creatinine increased > 1.5 – 6 x ULN
	
Withhold avelumab therapy Increase frequency of monitoring to every 3 days 1.0 to 2.0 mg/kg/day prednisone or equivalent. Add prophylactic antibiotics for opportunistic infections Consider renal biopsy
	
If returns to Baseline: Taper steroids over at least 1 month, and resume avelumab therapy following steroids taper. If worsens: Treat as Grade 4.

Grade 4 Creatinine increased > 6 x ULN
	
Permanently discontinue avelumab therapy Monitor creatinine daily 1.0 to 2.0 mg/kg/day prednisone or equivalent. Add prophylactic antibiotics for opportunistic infections Consider renal biopsy Nephrology consult
	
If returns to Baseline: Taper steroids over at least 1 month.

Cardiac irAES		

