Grade 2 or Grade 3 clinical signs or symptoms suggestive of a potential irAE	Withhold avelumab therapy pending clinical investigation	If irAE is ruled out, manage as appropriate according to the diagnosis and consider re-starting avelumab therapy If irAE is confirmed, treat as Grade 2 or 3 irAE
Grade 2 irAE or first occurrence of Grade 3 irAE	Withhold avelumab therapy 1.0 to 2.0 mg/kg/day prednisone or equivalent Add prophylactic antibiotics for opportunistic infections Specialty consult as appropriate	If improves to Grade 1: Taper steroids over at least 1 month and resume avelumab therapy following steroids taper
Recurrence of same Grade 3 irAEs	Permanently discontinue avelumab therapy 1.0 to 2.0 mg/kg/day prednisone or equivalent Add prophylactic antibiotics for opportunistic infections Specialty consult as appropriate	If improves to Grade 1: Taper steroids over at least 1 month
Grade 4	Permanently discontinue avelumab therapy 1.0 to 2.0 mg/kg/day prednisone or equivalent and/or other immunosuppressant as needed Add prophylactic antibiotics for opportunistic infections Specialty consult.	If improves to Grade 1: Taper steroids over at least 1 month

Requirement for 10 mg per day or greater prednisone or equivalent for more than 12 weeks for reasons other than hormonal replacement for adrenal insufficiency	Permanently discontinue avelumab therapy Specialty consult	
Persistent Grade 2 or 3 irAE lasting 12 weeks or longer		

ACTH: adrenocorticotropic hormone; ADL: activities of daily living; ALT: alanine aminotransferase; AST: aspartate aminotransferase; BNP: B-type natriuretic peptide; CK-MB: creatine kinase-myocardial fraction b; CT: computed tomography; FSH: follicle stimulating hormone; GH: growth hormone; IGF-1: insulin-like growth factor; irAE: immune-related adverse event; LH: luteinizing hormone; MRI: magnetic resonance imaging; NCI-CTCAE: National Cancer Institute Common Terminology Criteria for Adverse Event; T4: free thyroxine; TSH: thyroid-stimulating hormone; ULN: upper limit of normal.

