10.2 Protocol Deviations

10.2.1 Important Protocol Deviations (IPDs)

Important protocol deviations (IPDs) are protocol deviations that might significantly affect the completeness, accuracy, and/or reliability of the study data or that might significantly affect a participant's rights, safety, or well-being.

Important protocol deviations include:

- Participants enrolled and dosed on the study who did not satisfy enrolment criteria
- Participants that develop withdrawal criteria whilst on the study but are not withdrawn
- Participants that receive the wrong study intervention or an incorrect dose
- Participants that receive an excluded concomitant medication
- Failure to collect data necessary to interpret primary endpoints
- Failure to collect necessary key safety data
- Deviation from Good Clinical Practice (GCP)
- Any other protocol deviation that might significantly affect the completeness, accuracy, and/or reliability of the study data or that might significantly affect a participant's rights, safety, or well-being.

Important protocol deviations will be identified for all participants by either site monitoring, medical review processes or programming and confirmed prior to or at the Data Review Meeting at the latest.

All important protocol deviations are captured in SDTM datasets, whether identified through site monitoring, medical review or programming. The management of protocol deviations is outside of this IAP document.

IPDs will be listed for all subjects in the FAS.

IPDs will be determined for all subjects by either medical review processes or programming based on the inclusion/exclusion criteria or other criteria presented in the protocol.

The complete list of IPDs is maintained by the medical team in the Clinical Trial Management System (CTMS) and will be finalized prior to database lock.

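### Table 5's 12-week steroid trigger for permanent discontinuation is a flat 10 mg/day although the table's corticosteroid doses are per kg, so the smallest eligible children cannot reach it on those doses

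*Protocol*

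**What the plan says.** The last block of Protocol Table 5 (Section 6.5.5.3, other irAEs) requires permanent discontinuation and a specialty consult on a "Requirement for 10 mg per day or greater prednisone or equivalent for more than 12 weeks for reasons other than hormonal replacement" for adrenal insufficiency. No adjustment for weight, age or body surface is given.

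The corticosteroid treatment doses in the table are scaled to weight. The usual one is "1.0 to 2.0 mg/kg/day prednisone or equivalent", which also stands in the rows just above the trigger. The lowest is for persistent Grade 1 to 2 rash: "Consider 0.5 to 1.0 mg/kg/day prednisone or equivalent". The other immunosuppressants given with a dose are scaled to body size too: "Add infliximab 5 mg/kg (if no contraindication" and "Add mycophenolate mofetil 600 mg/m 2 (for subjects 2 to 18 years of age) twice daily".

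Next to the steroid trigger is a second one that does not depend on weight: "Persistent Grade 2 or 3 irAE lasting 12 weeks or longer".

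The population is "pediatric subjects 0 to < 18 years of age" (Protocol 5.1). The only weight cut in the documents is 10 kg, used to stratify PK sampling (Protocol 7.5) and PK summaries (SAP 16.1.2.2). SAP 11.1 has an age category below 1 year.

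SAP 10.1 tabulates treatment discontinuation by reason. SAP 10.2.1 counts as an important protocol deviation: "Participants that develop withdrawal criteria whilst on the study but are not withdrawn".

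**The concern.** A fixed number of milligrams is a different per-kg amount in every child. Two children with the same irAE, on the same mg/kg dose for the same time, can fall on opposite sides of a mandatory stopping rule because one weighs more. In the smallest eligible children the rule cannot operate at all on the doses the table prescribes. The documents give no reason for a flat figure in this one row.

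At stake are consistent handling of prolonged steroid need across a very wide weight range and, to a lesser extent, the meaning of two descriptive outputs: discontinuations by reason, and the listing of participants who met a withdrawal criterion but stayed on treatment. The second holds only if the trial team counts this Table 5 row as a withdrawal criterion, since Protocol 5.5.1 does not name it.

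**Working it through.** The plan gives no per-kg equivalent of the trigger, so there is no figure of its own to reproduce.

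**Inputs from Table 5.** Trigger T = 10 mg/day or more for more than 12 weeks. Prednisone treatment doses d = 0.5, 1.0 and 2.0 mg/kg/day. The severe hepatic and hypophysitis rows state the dose as methylprednisolone. They are left out because the documents give no conversion factor.

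**Step 1: weight below which dose d cannot reach T.** Weight = T/d.
- d = 2.0: 10/2.0 = 5 kg
- d = 1.0: 10/1.0 = 10 kg
- d = 0.5: 10/0.5 = 20 kg

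These limits use only the table's figures. No weight has to be assumed.

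**Step 2: trigger per kg, and daily dose by weight.** Trigger per kg = 10/weight; daily dose = d × weight. The weights are illustrative.

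| Weight (kg) | 10 mg/day as mg/kg/day | mg/day at 0.5 mg/kg | mg/day at 1.0 mg/kg | mg/day at 2.0 mg/kg |
|---|---|---|---|---|
| 3 | 3.33 | 1.5 | 3 | 6 |
| 4 | 2.50 | 2 | 4 | 8 |
| 5 | 2.00 | 2.5 | 5 | 10 |
| 7.5 | 1.33 | 3.75 | 7.5 | 15 |
| 10 | 1.00 | 5 | 10 | 20 |
| 20 | 0.50 | 10 | 20 | 40 |
| 60 | 0.17 | 30 | 60 | 120 |

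Under 5 kg nothing in the 1.0 to 2.0 mg/kg/day range reaches 10 mg/day. At 5 kg only the top of the range does. At 60 kg the trigger is met at 10/60 = 0.167 mg/kg/day, one sixth of the 1.0 mg/kg/day dose.

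**Step 3: ratio of strictness between two children.** This is the ratio of their weights: 60/20 = 3, 60/10 = 6, 60/5 = 12, 60/3 = 20.

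**Step 4: which cases the other rules already settle.**
- Grade 4, or recurrence of the same Grade 3 irAE (other-irAE rows): permanent stop at any weight.
- Grade 2 or 3 lasting 12 weeks or more: covered by the neighbouring row at any weight. Its action cell is blank in the text available to me; I read it as merged with the steroid row, that is, permanent discontinuation.
- Grade 1, but only while steroids continue beyond 12 weeks: the neighbouring row does not apply, so the steroid row decides. At 1.0 mg/kg/day a 7.5 kg child takes 7.5 mg/day and does not meet it; a 20 kg child takes 20 mg/day and does.

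In that third case avelumab is usually not being given at the time, because most rows that prescribe steroids and allow resumption allow it only after the taper. The weight-dependent outcome is therefore mainly permanent discontinuation against remaining eligible to resume.

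**The case against.** The strongest case against the point is that a treatment dose and a steroid-dependence threshold are different quantities, so different scales are not in themselves a conflict, and that the table protects small children in other ways. Much of this stands.

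A reader might infer that body size alone decides who stays on avelumab. The documents do not support that. The 12-week persistence row, the Grade 4 rule and the recurrent Grade 3 rule apply at any weight, and Protocol 5.5.1 lets the investigator stop treatment for safety.

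A reader might also infer that infants could receive avelumab through months of high-dose steroids. For Grade 3 colitis, persistent or Grade 3 rash, Grade 2 pneumonitis, Grade 2 hepatic, Grade 2 to 3 renal and other irAEs, Table 5 holds avelumab and resumes it only after the taper. The hypophysitis row is the exception: it prescribes steroids without stating that wait. Under Protocol 5.1.3.2, resuming after more than 2 skipped doses for a Grade 2 ADR also needs Medical Monitor consultation.

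Nor are all doses in the table per kg. Mycophenolate is per m². The statement is true of corticosteroids.

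Finally, no effect on dose finding follows. The trigger needs more than 12 × 7 = 84 days and the DLT window is 28 days. Phase I is small (12 to 36 subjects planned), its first 3 subjects are at least 1 year old, and nothing shows that a child under 5 kg was expected or enrolled.

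What the objection does not remove is the Grade 1 case in step 4. A rule on steroid requirement adds something to the persistence row precisely when steroids are what keeps the grade down, and there it works in larger children and not in the smallest ones.

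**Conclusion.** The point holds in a narrow form. The trigger is flat, every numerical corticosteroid dose in Table 5 is per kg, and the two do not fit together across the eligible range. On the table's prednisone doses the trigger is out of reach under 10 kg at 1.0 mg/kg/day and under 5 kg at 2.0 mg/kg/day. These limits are exact for a child dosed as the table directs; a child given more than the table's range could still meet the trigger.

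The 3-, 12- and 20-fold figures depend on assumed weights. None of them is a property of the rule by itself.

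The consequence is mostly permanent stop versus eligibility to resume for a child whose irAE is held at Grade 1 by prolonged steroids. The documents do not allow an estimate of how many children that is. No efficacy estimate, DLT rate or MTD decision is shown to be affected. This is an inconsistency to correct, and not a threat to the trial's conclusions.

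**What to change.** Reconcile the flat steroid-requirement row with the per-kg corticosteroid doses in Table 5, so that the rule can be applied across the whole eligible age and weight range. The basis and value are for the sponsor's clinicians, and none is proposed here. It would help to state at the same time how the row relates to the neighbouring 12-week persistence row, and whether it counts as a withdrawal criterion for SAP 10.2.1.

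The cost is one table row in a protocol amendment, with no change to sample size or analysis. The SAP modification history (version 2.0, June 2021) records that evaluation of avelumab monotherapy in pediatric patients ended after Phase I. If an amendment is no longer practical, a sentence in the clinical study report can say that meeting this trigger depended on body weight, and the row should be reconciled before the table is reused in another pediatric protocol.

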## 6.6 Packaging and Labeling of the Investigational Medicinal Product

Avelumab is formulated as a 20.0 mg/mL solution and is supplied by the Sponsor in single-use glass vials, stoppered with a rubber septum and sealed with an aluminum/yellow polypropylene flip-off seal.

Avelumab will be packaged and labeled in accordance with all applicable regulatory requirements and Good Manufacturing Practice guidelines. Each box of avelumab will contain 1 vial. The information on the label will be in accordance with approved submission documents.

Avelumab will be shipped in suitable transport containers according to its storage and shipping conditions. Shipments are monitored with temperature control devices.

CCI [REDACTED]

The contents of the avelumab vials are sterile and nonpyrogenic, and do not contain bacteriostatic preservatives. Any spills that occur should be cleaned up using the facility's standard cleanup procedures for biologic products.

Avelumab must be stored at CCI [REDACTED] until use, with a temperature log maintained daily. All medication boxes supplied to each trial site must be stored carefully, safely, and separately from other drugs.

Avelumab stored at room temperature CCI [REDACTED] or at elevated temperatures CCI [REDACTED] for extended periods is subject to degradation. Avelumab must not be frozen. Rough shaking of avelumab must be avoided.

For application in this trial, avelumab must be diluted with 0.9% saline solution (sodium chloride injection) or as indicated in the Pharmacy Manual. Detailed information on infusion bags and medical devices to be used for the preparation of the dilutions and subsequent administration will be provided in the Pharmacy Manual.

Avelumab must not be used for any purpose other than the trial. The administration of avelumab to subjects who have not been enrolled into the trial is not covered by the trial insurance.

Any unused portion of the solution should be discarded in biohazard waste disposal, with final disposal by accepted local and national standards of incineration.

Storage, handling, preparation, and disposal of avelumab should be according to local institutional guidelines.

## 6.8 Investigational Medicinal Product Accountability

The Investigator is responsible for ensuring accountability for trial drug, including reconciliation of drugs and maintenance of drug records.

- Upon receipt of trial drug, the Investigator (or designee) will check for accurate delivery and acknowledge receipt by signing (or initialing) and dating the documentation provided by the Sponsor and returning it to the Sponsor. A copy will be retained for the Investigator Site File.
- The dispensing of the trial drug will be carefully recorded on the appropriate drug accountability forms provided by the Sponsor, and an accurate accounting will be available for verification by the Sponsor's Monitor at each monitoring visit.
- Trial drug accountability records will include:
  - confirmation of trial drug delivery to the trial site.
  - the inventory at the site of trial drug provided by the Sponsor and prepared at the site.
  - the use of each dose by each subject.
  - dates, quantities, batch numbers, expiry dates and (for trial drug prepared at the site) formulation, as well as the subjects' trial numbers.
- The Investigator should maintain records that adequately document that:
  - the subjects were provided the doses specified by the clinical trial protocol.
  - all trial drug provided by the Sponsor was fully reconciled.

Unused trial drug must not be used for any purpose other than the current trial. Any trial drug that has been dispensed to a subject must not be redispensed to a different subject.

The Sponsor's Monitor will periodically collect the trial drug accountability forms and will check all returns (both unused and used containers) before arranging for their return to the Sponsor or authorizing their destruction by the trial site.

At the conclusion or termination of this trial, trial site personnel and the Clinical Trial Monitor will conduct a final product supply inventory on the Investigational Drug Accountability Forms, and all unused containers will be destroyed. Instructions for destruction of product will be provided to the site. The Clinical Trial Monitor will be supplied with a copy for filing of the Investigational Drug Accountability Forms. This documentation must contain a record of clinical supplies used, unused, and destroyed and shall include information on:

- all administered units.
- all unused units.
- all destroyed units (during the trial).
- all destroyed units at the end of trial.
- date of destruction(s).
- name and signature of the Investigator/pharmacist.

It must be ensured at each trial site that the trial drug is not used:

- after the expiry date.
- after the retest date unless the trial drug is reanalyzed and its retest date extended.

This is to be closely monitored by the Clinical Trial Monitor.

## 6.9 Assessment of Investigational Medicinal Product Compliance

In this trial, subjects will receive trial treatment at the investigational site. Well-trained medical staff will monitor and perform the trial drug administration. The information of each trial drug administration, including the date, time, and dose of trial drug, will be recorded on the eCRF. The Investigator will make sure that the information entered into the eCRF regarding drug administration is accurate for each subject. Any reason for noncompliance should be documented.

Noncompliance is defined as a subject missing > 1 cycle of trial treatment for nonmedical reasons and barring any extenuating circumstances in the opinion of the Investigator. If 1 cycle was missed, and the interval between the subsequent treatment cycle and the last administered treatment cycle was longer than 4 weeks for nonmedical reasons, the criteria of insufficient compliance are met as well.

## 6.10 Blinding

This is an open-label trial. Therefore, trial treatment is not blinded.

## 6.11 Emergency Unblinding

Not applicable.

## 6.12 Treatment of Overdose

An overdose is defined as any dose 5% or more than the calculated dose for that particular administration. Any overdose must be recorded in the trial drug section of the eCRF.

For monitoring purposes, any case of overdose, whether or not associated with an AE (serious or nonserious), must be reported to Drug Safety in an expedited manner using the SAE Report Form (see Section 7.4.1.4).

There are no known symptoms of avelumab overdose to date. The Investigator should use his or her clinical judgment when treating an overdose of the trial drug.

